## C STATISTICAL METHODS AND ANALYSIS

The SURTAVI trial is a multicenter, multinational, prospective, adaptive, 1:1 randomized study designed to demonstrate non-inferiority (to within an absolute margin of 0.07) of TAVI to SAVR, as measured by a composite of all-cause death or disabling stroke incidence at 24 months. Study success will be evaluated at an interim analysis that is timed to occur when 1400 subjects who undergo an attempted study treatment have reached 12 months; if necessary, study success will again be evaluated when all subjects have reached 24 months.

A study report will be prepared for submission to FDA at the time study success criteria have been met, for the purpose of seeking marketing approval. After all subjects have completed all protocol-specified follow-up, a final clinical report including updated long-term safety data will be prepared and submitted.

Roll-in subjects (refer to CIP section C.4.4) will not be included in the primary or secondary analysis; however, the data will be summarized separately with descriptive statistics.

Any deviations from this section and/or the Statistical Analysis Plan will be described and justified in the Final Report, as appropriate.

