**C.4.2 Randomization, Sample Size, and Analysis Plan**

Randomization will follow a 1:1 (treatment:control) allocation ratio and be stratified by site and need for revascularization, using a blocked randomization scheme with blocks of randomly varying sizes. The sample size for the mITT population is 1600 subjects.

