#### C.4.2.2 Analysis Plan

The sample size look analysis (timed when 1400 subjects had entered the mITT population) occurred prior to the change of margin; the conclusion of this analysis was that 1400 would be inadequate to establish non-inferiority (using  $\delta = 0.05$ ) and that subject accrual should continue (refer to Appendix G.1 for sample size determination algorithm). With the re-design accompanying the change of margin, an interim analysis (timed to occur when 1400 mITT subjects have reached 12 months) for the purpose of declaring an early win will occur and all enrolled mITT subjects will be included in the analysis. At this analysis, if  $P(H_{\delta=0.07} | \text{data}) > \Psi$ , non-inferiority will be declared at this time, and a regulatory submission will follow. On the other hand, if  $P(H_{\delta=0.07} | \text{data}) \leq \Psi$ , all mITT subjects will be followed to 24 months, when a final analysis will occur. At the final analysis, the standard for trial success will again be  $P(H_{\delta=0.07} | \text{data}) > \Psi$ . These two analyses are termed “Win Looks”.

If, at the early interim “Win Look,” non-inferiority is established, a test of superiority will immediately follow. If  $P(H_{\delta=0} | \text{data}) > \Psi_{\text{SUP}}$ , superiority will be established at this time. However, if  $P(H_{\delta=0} | \text{data}) \leq \Psi_{\text{SUP}}$ , subjects will continue to be followed and analyzed according to the same analysis plan (i.e., with one more possible “Win” analysis when all mITT subjects have reached 24 months). At the final “Win” analysis, if  $P(H_{\delta=0} | \text{data}) > \Psi_{\text{SUP}}$ , a delayed determination of superiority will be made.

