The statistical approach for these analyses is Bayesian. The prior distributions for  $\pi_T$  and  $\pi_C$  in these calculations are Beta(1,1). The threshold  $\Psi$  is designated to be 0.971 for non-inferiority testing and  $\Psi_{\text{SUP}} = 0.989$  for superiority testing; these values were selected by trial-and-error to achieve a type I error (under extensive simulation) of at most 0.05 for non-inferiority testing and at most 0.025 for superiority testing under the design with  $\delta = 0.05$  margin. These same thresholds are retained in the current study design. Control of type I error using these thresholds is described in detail in “Type I Errors” (Section C.7.5). Of note, establishing  $P(H_{\delta=0} | \text{data}) > \Psi_{\text{SUP}}$  means that superiority has been established to a standard equivalent to a nominal significance level of 0.025 (1-sided), but this does not automatically mean that a labeling claim of superiority is supported. See “Multiplicity Considerations” (Section C.12) for additional requirements regarding labeling claims on secondary objectives.

---

 Jennison C and Turnbull BW, Group Sequential Methods with Applications to Clinical Trials. Boca Raton: Chapman & Hall, 2000, p 27

 Medtronic CoreValve SURTAVI Trial 2014 FDA Annual Progress Report.

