**Table 3: Operating characteristics of the design when  $\pi_C = 0.17$ , from a simulation of 10,000 simulated trials per line. Interpretations of column headings are given in the narrative**

$\pi_C = 0.17$				Probability of Achieving Sample Size N	
Diff ( $\pi_T - \pi_C$ )	Power	Early Win, Late Win	Average N	N=1400 (Promise, Futile)	N=1600
-0.025	0.9954	0.9909 0.0045	1446.8	0.7615 0.0043	0.2342
0	0.9402	0.8896 0.0506	1509.1	0.4146 0.0401	0.5453
0.025	0.6410	0.5338 0.1072	1536.1	0.1425 0.1768	0.6807
0.05	0.1974	0.1505 0.0469	1506.5	0.0268 0.4406	0.5326
0.07	0.0409	0.0329 0.0080	1465.0	0.0050 0.6700	0.3250
0.075	0.0218	0.0158 0.0060	1454.3	0.0033 0.7253	0.2714

In Table 3, the type I error rate (when  $\pi_T - \pi_C = 0.07$ ) is 0.0409. In this scenario, the trial went to its maximum size of N=1600 32.50% of the time, often stopping accrual sooner for futility (0.6700), and only rarely stopping accrual early for promising trend (0.0050). Those trials that either stopped early for promising trend or went to the maximum of 1600 were tested for an "early win" twelve months after accrual stops, with 3.29% (of the 10,000) winning early and an additional 0.80% winning at the final analysis (for a total type 1 error rate of 0.0409). When  $\pi_T - \pi_C = 0$ , the estimated power is 94.02%; the trial stopped accruing for promising trend at N=1400 41.46% of the time; the maximum of N=1600 occurred 54.53% of the time. The proportion of trials that passed at the interim "win" analysis was 88.96%, while an additional 5.06% passed the primary objective at the final "win" analysis. The average of the sample sizes (across the 10,000 simulated trials) was 1509.1 subjects, which is an average of some trials that stop accrual at N=1400 and some that stop at N=1600.

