### C.7.2 Control Arm Event Rate

A stated assumption made in the operating characteristics as displayed in Table 3 is that the control arm event rate is  $\pi_C = 0.17$ . Alternative scenarios were simulated in which the control arm event rate was instead 12% and 22%. The results of these simulations are provided below in Table 4. It is evident that the type I error is  $< 0.05$ . Power is  $> 95\%$  when  $\pi_T - \pi_C = 0$  and  $\pi_C = 0.12$  and  $> 80\%$  when  $\pi_T - \pi_C = 0$  and  $\pi_C = 0.22$ .

**Table 4: Operating characteristics of the design under differing control arm event rate assumptions. 10,000 simulated trials per line, with predictions based on 5000 imputations. Column interpretations are the same as in Table 3**

$\pi_C = 0.12$				Probability of Achieving Sample Size N	
Diff ( $\pi_T - \pi_C$ )	Power	Early Win, Late Win	Average N	N=1400 (Promise, Futile)	N=1600
-0.025	0.9994	0.9989 0.0005	1424.8	0.8753 0.0006	0.1241
0	0.9778	0.9549 0.0229	1493.2	0.5177 0.0163	0.4660
0.025	0.7455	0.6417 0.1038	1540.1	0.1713 0.1283	0.7004
0.05	0.2443	0.1857 0.0586	1512.9	0.0284 0.4069	0.5467
0.07	0.0407	0.0311 0.0096	1463.3	0.0055 0.6781	0.3164
0.075	0.0243	0.0192 0.0051	1454.1	0.0028 0.7265	0.2707
$\pi_C = 0.22$				Probability of Achieving Sample Size N	
Diff ( $\pi_T - \pi_C$ )	Power	Early Win, Late Win	Average N	N=1400 (Promise, Futile)	N=1600
-0.025	0.9872	0.9752 0.0120	1464.4	0.6670 0.0108	0.3222
0	0.8971	0.8277 0.0694	1517.7	0.3519 0.0598	0.5883
0.025	0.4702	0.4702 0.1071	1535.7	0.1188 0.2029	0.6783
0.05	0.1861	0.1424 0.0437	1503.6	0.0260 0.4558	0.5182
0.07	0.0388	0.0305 0.0083	1463.2	0.0053 0.6787	0.3160
0.075	0.0270	0.0204 0.0066	1454.7	0.0044 0.7219	0.2737

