This mechanism of generating temporally correlated data represents the sponsor's best knowledge and belief about the data that will actually arise in the prospective clinical trial. All operating characteristics in Table 3, Table 4, and Table 5 are generated with this method.

This mechanism only applies to the *generation of artificial* data in the simulation; it is not used at all in the analysis of data (real or simulated). If this data generation model does not adequately reflect the true pattern of serial correlation, the analysis model will nonetheless be tasked with recognizing this and causing the design to respond appropriately. In order to evaluate the robustness of the analysis model and sampling plan to the pattern of serial correlation, a simulation was conducted wherein the study design was presented with data simulated at the extremes of complete temporal correlation and complete temporal independence.

"Complete Temporal Correlation" is a scenario in which knowing the 1-month outcome for a subject is the same as knowing the 24-month outcome. This is accomplished by setting all interim outcomes (eg., 1-month, 6-month, etc.) to be equal to the 24-month "E" or "N" outcomes (except for those patients lost to follow-up in the simulation). The study design is expected to react appropriately and much sooner when presented with this pattern of data. "Complete Temporal Independence" is a scenario where knowing the interim outcomes for a subject gives no information about what that subject will be at 24 months. To accomplish this, no patient can be an "E" prior to 24 months (else there would be serial correlation), and subject outcomes at interim time points are set to be "P" or "N" with probability  $P(E24)$ , independently at each time point.

Table 9 displays operating characteristics generated under the Complete Temporal Correlation and Complete Temporal Independence patterns. As expected, the design reacts quicker (ie., with smaller sample size and higher chance of early win) when the data are completely correlated. While neither scenario is particularly realistic, it is important that the observed Type I errors are  $< 0.05$  in both cases and the powers are acceptable.

**Table 9: Operating characteristics of the design under alternative assumptions about temporal correlation. 10,000 simulated trials per line, with predictions based on 5000 imputations. Column meanings are the same as in Table 3**

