### C.12 Multiplicity Considerations

It is recognized that with a multiplicity of tests comes an inflation in the chance of a false finding of superiority or non-inferiority. Therefore, for the purpose of seeking approved labeling claims on designated secondary objectives, the following standard will be used: If the primary objective demonstrates non-inferiority, claims will be sought for selected secondary non-inferiority and superiority objectives and for superiority on the primary objective metric. These will be tested via a hierarchical (sequential) testing order that preserves the overall study-wise type I error rate at the level of 0.05, while requiring all non-inferiority tests to meet a nominal type I error rate of 0.05 and all superiority tests to meet a nominal type I error rate of 0.025. The testing order is specified below. The following objectives are tested in order, and testing continues if and only if all previous objectives have met their designated success criterion.

1. Primary endpoint (non-inferiority)
2. Transvalvular mean gradient at 12 months (non-inferiority)
3. Effective orifice area at 12 months (non-inferiority)
4. Change in NYHA classification from baseline to 12 months (non-inferiority)
5. Change in KCCQ score from baseline to 30 days (non-inferiority)

All of the above are non-inferiority tests and are tested with a type I error standard of 0.05. If all of the above tests meet their success criterion, the type I error rate of 0.05 that is passed on from the above tests will be split equally (using a Bonferroni justification) between the following parallel subfamilies, so that each subfamily is tested using a type I error rate of 0.025:

---

10 Berry D & Lindgren B, *Statistics: Theory and Methods*, 2ed. Belmont, CA: Duxbury, 1996, p 505.

11 Conover WJ & Iman RL, "Rank transformations as a bridge between parametric and nonparametric statistics," *American Statistician* 35 (1981), 124-129.

Subfamily #1: Primary endpoint (superiority)

Subfamily #2: Secondary (superiority) objectives #5–#18 as enumerated below, tested in ordered sequence such that all  $\alpha$  is passed on to subsequent tests if a test criterion is met, while all testing stops if a test criterion is not met. This procedure controls the type I error rate of this subfamily at the level 0.025.

It is not necessary to “pass” all objectives in one subfamily in order to test the objective(s) in the other subfamily.

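### SAP V6 quotes error and power for a design that can still stop at 1400, not for the 1600-subject trial that remains; one type I error statement and one power entry are also wrong

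*Combined protocol and SAP*

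**What the plan says.** All references are to SAP V6.

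- **Threshold.** C.4.2.2 sets Psi = 0.971 for non-inferiority. It was found by trial and error to hold type I error at 0.05 under the margin of 0.05, and then kept: "These same thresholds are retained in the current study design".
- **Status of the 1400 look.** C.4.2.2 reports that it was done before the margin changed, and "the conclusion of this analysis was that 1400 would be inadequate to establish non-inferiority" at the margin of 0.05. Accrual went on. C.4.2 now fixes the size: "The sample size for the mITT population is 1600 subjects".
- **What is simulated.** C.6 describes a look at 1400 with margin 0.05, then two Win Looks with margin 0.07. Table 3 (control rate 0.17) gives type I error 0.0409 and power 0.9402.
- **Statements of control.** Introducing Table 9, C.7.4 says "it is important that the observed Type I errors are" below 0.05 at both correlation extremes. C.12 says the testing order "preserves the overall study-wise type I error rate at the level of 0.05".
- **Disclosure.** C.7.5 reports that independence with fast accrual has the highest error and calls that combination implausible. It adds that expected-correlation cells stay well below 0.05.

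**The concern.** Primary non-inferiority gates every labeling claim in C.12, and Psi is its only decision threshold. The evidence that Psi = 0.971 holds 0.05 comes from tables in which most null trials are removed at 1400 and so can never win. The rule that removes them uses the stricter margin of 0.05, while wins are judged at 0.07. That rule has already been applied and cannot protect the trial again. No table shows 1600 subjects with no stop. In addition, one sentence about error control disagrees with the table it introduces.

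**Working it through.** **1. Text against tables.** Table 9 gives 0.0516 under independence, so the C.7.4 sentence is wrong as written. Table 12, independence rows, at control rates 0.12 / 0.17 / 0.22:

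| Accrual | Type I error |
|---|---|
| Slow | 0.0453 / 0.0488 / 0.0447 |
| Expected | 0.0546 / 0.0516 / 0.0534 |
| Fast | 0.0618 / 0.0638 / 0.0621 |

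C.7.5 sets the limit for simulation noise at 0.05 + 1.96 × √(0.05 × 0.95 / 10,000) = 0.0543. Four cells exceed it. The expected-accrual row pools to (0.0546 + 0.0516 + 0.0534)/3 = 0.0532. With 30,000 trials the standard error is 0.00126, so z = 0.0032/0.00126 = 2.5.

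**2. Stops credited in Table 3.** At a true difference of 0.07: 0.6700 (futility) + 0.0050 (promise) = 0.6750. At zero difference: 0.4146 + 0.0401 = 0.4547.

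**3. Reproducing the SAP design.** Inputs: Table 8 skeletons with the logit shift; Table 2 priors at the 1400 look; the Table 13 limits for that look (0.05 and 0.80, futility projected to 2000); flat priors at the Win Looks; Psi = 0.971; 6% uniform dropout; C.7.3 accrual. The re-simulation used a normal approximation, with 20,000 trials per null scenario and 10,000 per power scenario.

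| Quantity (control rate 0.17) | SAP | With the 1400 stops | No stop, N = 1600 |
|---|---|---|---|
| Type I error, expected correlation and accrual | 0.0409 | 0.0425 | 0.047 |
| Type I error, independence, expected accrual | 0.0516 | 0.0541 | 0.059 |
| Power at zero difference, expected correlation and accrual | 0.9402 | 0.943 | 0.967 |

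A second run of 6,000 trials per scenario gave 0.048, 0.058 and 0.969 for the last column. The match to the SAP is good for error and power but looser for the stopping step: 0.481 of zero-difference trials stopped for promise, against 0.4146. The no-stop column does not use that step.

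The Monte Carlo standard error of the 0.047 is √(0.047 × 0.953 / 20,000) = 0.0015, so the planning scenario is below 0.05 by a thin margin.

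No-stop power at control rates 0.12 and 0.22 is 0.992 and 0.933 (SAP 0.9778 and 0.8971).

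**4. Which accrual curve applies.** The monthly counts listed in C.7.3 for months 1-21 sum to 576. Enrolment began in June 2012, and V6 is dated 31 May 2016, the end of month 48. Totals by then:

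- slow: 576 + 27 × 30 = 1,386
- expected: 576 + 27 × 45 = 1,791
- fast: 576 + 27 × 60 = 2,196 (2,181 if the faster rate starts in month 23)

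The revision history reports approximately 1600. If accrual was not paused, the real curve lies between slow and expected. Under independence at control rate 0.17 the no-stop error is then between 0.052 (slow) and 0.059 (expected).

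**5. Psi needed for 0.05 with no stop.** Planning scenario: about 0.969-0.970, so 0.971 suffices. Independence with expected accrual: about 0.976-0.977. At control rate 0.17, power at Psi = 0.976 is 0.959 (0.964 in the second run).

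**6. Table 4, control rate 0.22, difference 0.025.** The early and late wins are "0.4702 0.1071", which sum to 0.5773. The power column repeats 0.4702. Other rows of that block add up, for example 0.8277 + 0.0694 = 0.8971.

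**The case against.** The sponsor's case is substantial.

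- **Control holds where the trial is planned.** All nine expected-correlation cells in Table 12 are between 0.0381 and 0.0461, and no complete-correlation cell exceeds 0.0305. Without the stop the planning figure remains below 0.05. A reader might infer that error control fails in general; the documents do not support that.
- **Independence is not realistic.** It allows no event before 24 months, whereas Table 16 shows one-year mortality of 10.9% and 13.2% in the intermediate-risk cohort. This stands as a limit on the weight of those cells. It does not make the C.7.4 sentence true, and the C.7.5 comment on Table 12 singles out the fast-accrual combination, not the three expected-accrual cells.
- **Fast accrual did not happen.** Three of the four cells above 0.0543 need it. A reader might infer that Psi should be set by those cells; step 4 argues against that.
- **Counting the look is legitimate.** It took place, and C.6 defines the design as including it. The tables are right for that design. But the whole design was not fixed in advance, because the margin changed after the look. A no-stop table is therefore needed beside them.
- **The conditional risk is not a type I error.** From Table 3, the chance of a false win given continuation lies between (0.0409 − 0.0050)/0.3250 = 11.0% and 0.0409/0.3250 = 12.6%. A reader might set this against 0.05. Any design with a futility look raises such a figure, so 0.05 is not its benchmark.

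**Conclusion.** The point holds in a limited form. The tabulated operating characteristics belong to a design with a stop that can no longer occur. For the trial that remains, type I error is about 0.047 in the planning scenario, about 0.006 above the quoted figure but within 0.05. It is about 0.058-0.059 under independence with expected accrual. Power is about 0.967, so the quoted power errs on the safe side. The C.7.4 sentence contradicts Table 9, though 0.0516 alone is within the SAP's noise limit. The Table 4 power is a copying error that affects no conclusion. The unqualified 0.05 claim in C.12 is stronger than the simulations allow.

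The no-stop figures assume the SAP's skeletons, dropout and accrual curves, and rest on a normal approximation with a Monte Carlo standard error of about 0.0015-0.002. The sponsor's own code should replace them.

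**What to change.** Before the Win Look:

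1. Re-run the non-inferiority tables (3-5, 9 and 12) at N = 1600 with no stop at 1400 and the actual accrual curve. Show them beside the existing whole-design tables. If the risk given continuation is reported, label it as conditional.
2. Either justify Psi = 0.971 on those results or raise it modestly; about 0.976 would cover independence at expected accrual. State the power cost at control rates 0.12, 0.17 and 0.22. At 0.17 it is about 0.8 points (0.967 to 0.959). At 0.22 power is about 0.933 before any increase, so the cost there must be shown.
3. Correct the C.7.4 sentence to agree with Table 9, and the Table 4 entry to 0.5773.
4. In C.12, describe control at 0.05 as approximate and dependent on the correlation scenario.

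The cost is one simulation re-run and text changes, with no added subjects or follow-up.

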## C.5 Predictions

Outcomes at 24-month are binary and are denoted "E" (for having experienced an Event) or "N" (for not having experienced an event). Predicted values of 24-month outcomes for those subjects who have not yet yielded 24-month outcomes will be based on intermediate outcomes observed at 1 month, 6 months, 12 months, and 18 months. These intermediate outcomes are:

[figure not shown]
- "E" -- subject has had a known primary event (death or disabling stroke) at the time point in question
- "P" -- subject is known to have had a "possible primary event" at the time point in question. "Possible primary events" are adverse events that may later be determined to be Disabling Strokes. This determination takes 90 days, by definition. For example, a subject may have a stroke at month 5 which cannot be known to be a Disabling Stroke until Month 8. At Month 6, such a subject is in the "P" state.
- "N" -- subject has not had a primary event or a "possible primary event" at the time point in question.

Subjects without 24-month outcome data will thus be considered to be in one of 26 states (13 for each treatment group). The 13 states are:

- no interim data
- E or P or N at 1 month, no subsequent data
- E or P or N at 6 months, no subsequent data
- E or P or N at 12 months, no subsequent data
- E or P or N at 18 months, no subsequent data

Subjects in the "E" state at an interim analysis can be imputed to be "E" at 24 months, with certainty. For each of the remaining 18 states (9 for each treatment group), the probability of becoming an "E" at 24 months is modeled via a Beta(a,b) prior distribution which is updated to a Beta(a+X, b+Y) distribution, based on the number X and Y of subjects who went on from that state to become 24-month "E" and "N" subjects, respectively. For example, if, in the treatment group at an interim analysis time point, it is known that 10 of 30 subjects had previously gone from the "N at 18 months" state to the "E at 24 months" state, then the transition probability from the 18-month "N" state to the 24-month "E" state will be modeled as Beta(a+10, b+20). At an interim analysis time point, any treatment-group subjects residing in the "N-at-18-month-but-without-24-month-data" state will have their 24-month outcome predicted on the basis of this Beta(a+10, b+20) distribution. Similar statements can be made about each of the possible transitions. As data are accrued in this study, the Beta distributions used for prediction are updated accordingly. Figure 1 graphically depicts the various possible states and transitions from them to the final state, for a generic treatment group. For clarity, the lines connecting the interim "E" state to the 24-month "E" state have been omitted. The numerical example above would apply to transition #9 in the Figure 1.

**Figure 1 Graphical depiction of transitions from interim states (E = Event, P = Possible Event, N = No Event, Start) to 24-month outcome. Each transition is assigned a separate Beta(a,b) prior distribution which is updated as data are gathered.**

By predicting 24-month outcomes for each of these states, and combining with the data from subjects with known 24-month outcomes, a **posterior probability of non-inferiority** is calculated; it is based on observed 24-month data and also a predictive model that employs interim outcomes and the relationship between those interim outcomes and their corresponding final outcomes that is *learned during the current trial*. This is accomplished in Monte Carlo fashion. With any one imputation of incomplete data, we calculate the posterior probability  $\Pr(H_{\delta=\delta^*} \mid \text{Observed 24-month Data, Imputed 24-month Data})$ , and store it. By iterating this process and averaging these posterior probabilities, we are essentially integrating them over the predictive distribution of imputed data. This resulting quantity we have denoted as  $\Pr(H_{\delta=\delta^*} \mid \text{Data})$ . The model is very similar to that employed in Lipscomb et al. The chief differences are that this model incorporates interim outcomes at other time points (eg., 1 month, 6 months, 18 months rather than just 12 months), and the model also considers trichotomous rather than dichotomous interim states.

The **predictive probability of eventual trial success** can be calculated in a similar manner. With any one imputation of incomplete data, we calculate the posterior probability  $\Pr(H_{\delta=\delta^*} \mid \text{Observed 24-month Data, Imputed 24-month Data})$  and record whether this value exceeds the threshold  $\Psi$ . By iterating this process and reporting the proportion of times that  $\Psi$  is exceeded, we obtain an estimate of the predictive probability of eventual trial success (meaning a trial that results in a conclusion of non-inferiority with the designated sample size).

In this trial, predictive probabilities of eventual success are used in the 1400-subject sample size analysis. Posterior probabilities are used for the determination of non-inferiority (ie., analyses in the evaluation portion of the trial or "Win Looks").

In any analysis conducted for the purpose of determining whether the primary endpoint has passed (ie, any "Win" analysis), no subject can be a "P" at 24 months. Whether a stroke

qualifies as a disabling stroke (primary endpoint) is accomplished via the Modified Rankin Score (mRS), which may take up to 3 months after the stroke's onset to determine, but all P's at 24 months will be converted to E's or N's. If at the precise time of a Win analysis there are any subjects who are still "P" at 24 months, Medtronic will wait until all such determinations and conversions are made before submitting the results, and thus there can be no P's at 24 months.

Sample Size Determination analysis is similar but with one small difference. If, at the precise time of a Sample Size Determination analysis, there are any subjects who are still "P" at 24 months, Medtronic may proceed with the Sample Size Determination analysis, treating each P in the TAVI or SAVR group as an E or an N in four separate analyses:

- each P in the SAVR group as an N and each P in the TAVI group as an E
- each P in the SAVR group as an N and each P in the TAVI group as an N
- each P in the SAVR group as an E and each P in the TAVI group as an E
- each P in the SAVR group as an E and each P in the TAVI group as an N

If the results of these analyses all imply the same decision about whether to stop enrolling, Medtronic will follow that decision. If the results imply differing decisions about whether to stop enrolling, no decision will be made until all 24-month P's have been resolved and converted to E's or N's.

